### 6.1.2. Qualitative data

Qualitative data	Type pf assessment

### 6.1.3. Baseline data

Registered at the inclusion visit (V0) by Investigator or a delegate hereof

- Date of informed consent (date)
- Date of visit (date)
- Check of inclusion criteria
- Check of exclusion criteria
- Subject number (number)

Demographic

- Date of birth (date)
- Gender (male/female)
- Height (number - cm)
- Weight (number – kg)

Stoma

- Age of stoma (year when created)
- Type of stoma (ileostomy/colostomy)
- Cause of the stoma (Crohn's disease/Colitis ulcerosa/ Cancer/ Other)
- Size of the stoma (diameter on widest place and height)
- Shape of the stoma (round/oval/irregular)
- Does your stoma change colour? (Yes/No)
  - If yes, please describe
- Does your stoma sometimes secrete excessively (weeping stoma)? (Yes/No)
  - If yes, please describe?
- Does your stoma change shape (change in diameter, change in length)? (Yes/No)
  - If yes, please describe?
- Does your stoma bleed regularly? (Yes/No)
  - If yes, please describe?
- Does your stoma change behaviour due to?
  - exercise? (Yes/No)
    - if yes, please describe
  - specific foods? (Yes/No)
    - if yes, please describe
  - hydration level? (Yes/No)
    - if yes, please describe
  - Other? (Yes/No)
    - If yes, please describe

Current product

- What is your Current product (brand, product name, item number, size, product type (1-piece))
- Are you used to cut the baseplate? (Yes/No)
  - If yes, how much is cut off from the baseplate (template of the baseplate where the cut is drawn upon, max cut in mm)?

Peristomal skin area

- How often do skin complications occur? (Daily, Every 2-3 days, Once a week, Once every second week, More rarely)
- Body profile with body check tool

#### Leakage/output

- What is the frequency of your output? (All the time (continuous)/with regular intervals/with irregular intervals)

#### 6.1.4. Rationale for selection and measurement of endpoints

The primary endpoint, TEWL, is a standardised non-invasive method for describing the barrier function of the skin. Damage to the skin surface will lower the barrier of the skin and thereby increase the water loss. This measurement is therefore used as primary endpoint

Additional skin measurements, assessments and the skin condition endpoints are all parameters describing the skin. Therefore, these are also essential to investigate if the new baseplate

The median wear time per subject in each period is used as endpoint, as it is considered a robust estimation of wear time.

Adverse events, device deficiencies, concomitant medication and safety questions comprise safety parameters. Qualitative interviews will give a subjective insight in the subject experience with the test product.

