### Test visits (V1, V2, V4, V5 and V6)

During test visit 1, the subject will be introduced to the clinical app on how to complete the questionnaires and take pictures. At visit 2 the test products will be handed out. At this visit the subjects will be trained according to the IFU, in preparation of the product (e.g. hole size), preparation of skin before application (e.g. cleaning and wiping), application of product (e.g. correct position and applying pressure to the baseplate), removal of product and storage of the product.

At each test visit objective skin measurement will be done, the product changed at the visit will be collected for further analysis, pictures of cut product will be taken, stoma condition, skin condition and safety endpoints will be registered. At test visit 2 and 6 questions regarding feeling of security, handling, leakage scale and quality of life will be completed by subject. An output sample will be collected for further analysis at test visit 1 and 2. The output samples and products changed at the visit will be stored in a separately CP300 allocated freezer at site, and send on an ongoing basis to Coloplast A/S, Humlebæk, Denmark. The samples of output will not be stored longer than it takes to collect and analyse the samples. The sample will be destroyed directly after analysis.

At test visit 6 questions about product preference will be completed by subject.

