### Product change

At every product change the subjects will record reason for change, pain/discomfort, skin condition and use of accessories. Wear time of the product will be calculated from the time for product change registered in the app.

At every product change the subject will be asked to take a picture of the back side of the changed products (leakage), the peristomal skin and the cut product to be applied. [REDACTED]

Subjects will also be informed about the possibility to contact a Coloplast nurse during the investigation, to ensure questions and experiences addressed answered properly. This will be a secondary contact person in addition to the study nurse at site.

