### **Safety follow-up**

To follow safety closely during the investigation, a safety visit (V3) is planned after one week of wearing the test product. The safety visit will, when logistically possible, be conducted by Sponsor at site, supported by Investigator or study nurse. The subjects will be asked about all experiences with their stoma during the investigation and other safety endpoints, following the safety interview guide (see Appendix 4). In addition, the product changed at the visit will be collected for further analysis.

To follow safety further, Sponsor might also wish to be presented at subjects' test visits. Sponsor will observe during the test visit and might ask the subject questions about experiences with their stoma during the investigation and other safety endpoints, following the safety interview guide (section 20.4).

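### As far as the visible text shows, median wear time includes wears cut short by site visits; at nominal lengths these are twice as frequent in Test Period 2, so the comparison leans against the test product

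*Combined protocol and SAP*

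**What the plan says.** Section 6.1.4 defines the endpoint: "The median wear time per subject in each period is used as endpoint". It justifies the choice by the robustness of the median.

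Section 6.4.1 (Product change) gives the derivation: "Wear time of the product will be calculated from the time for product change registered in the app". The same subsection says what else is captured: "At every product change the subjects will record reason for change, pain/discomfort, skin condition and use of accessories". No visible text uses the reason for change when wear time is calculated.

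Site visits also end wears. For V1, V2, V4, V5 and V6, section 6.4.1 says that "the product changed at the visit will be collected for further analysis". V3 adds another: "a safety visit (V3) is planned after one week of wearing the test product", and of that visit the plan says: "In addition, the product changed at the visit will be collected for further analysis".

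The flow-chart in section 6.4.4 shows the comparator handed out at V1. Section 6.4.1 has the test product handed out at V2. Section 6.3.3 spaces the visits after V2 about seven days apart.

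**The concern.** A wear that ends because the subject has come to the clinic measures the visit calendar, not how long the product lasts. Such a wear is usually shorter than it would otherwise have been. If both periods had the same share of these wears, both medians would shift by similar amounts and the contrast would be largely unaffected. The shares differ, because Test Period 2 has weekly visits and Test Period 1 has only its closing visit.

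The median is robust to a few extreme values. It is not robust to a one-sided change in the mix: when more of the intervals are short, the 50% point moves down. The order of products is fixed and there is no randomisation (section 6.4.6), so the artefact could not be told apart from a product effect unless it is handled by rule. At stake is a wear-time comparison that makes the test product look somewhat less durable than it is.

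**Working it through.** **1. The plan's own product count.** Section 6.2 expects one change per day: 14 days × 1 = 14 comparator products and 28 days × 1 = 28 test products. Both match the stated figures.

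**2. Visit-ended wears per period.** The product removed at V1 was applied before the comparator was handed out, so it is not a Period 1 wear. Period 1 therefore has one (V2). Period 2 has four (V3, V4, V5, V6).

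**3. Ratio of rates.** With period lengths L1 and L2, the ratio is (4/L2) ÷ (1/L1) = 4 × L1/L2.
- Nominal: 1/14 = 0.071 per day against 4/28 = 0.143 per day; 4 × 14/28 = 2.0. At daily change these are 7% and 14% of wears.
- Windows in section 6.1 (L1 from 12 to 29 days, L2 from 24 to 40 days): lowest 4 × 12/40 = 1.2, highest 4 × 29/24 = 4.8.
- Section 6.3.3 gives 12 to 39 days for Period 1, which does not agree with section 6.1. On that figure the top would be 4 × 39/24 = 6.5.
- Sites other than DK001 have V1 in weeks 49–51 and V2 in weeks 1–2, so Period 1 there will often exceed 14 days. At 22 days and a 28-day Period 2 the ratio is 4 × 22/28 = 3.1.

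**4. Hand check of the median at daily change.** Suppose that a share p of wears is cut short and that all of these fall below the median. The observed median then sits at natural quantile q = (0.5 − p)/(1 − p).
- Period 1: p = 1/14, q = 0.462, normal deviate −0.097.
- Period 2: p = 4/28, q = 0.417, normal deviate −0.210.
- Mean 1 day, CV 0.2: (1 − 0.2 × 0.210)/(1 − 0.2 × 0.097) = 0.958/0.981 = 0.977.

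**5. Simulation with identical products.** Assumptions: gamma wear times, capped at 3 days (the slowest change that section 6.1 permits); visit removals at day 14 in Period 1 and at days 7, 14, 21 and 28 in Period 2. The table shows the ratio of mean subject medians, Period 2 to Period 1. The true ratio is 1.

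| Mean wear, CV | Visit wears counted | Excluded | Censored (Kaplan-Meier) |
|---|---|---|---|
| 1.0 day, 0.2 to 0.4 | 0.978 to 0.960 | 0.98–1.00 | 1.00–1.01 |
| 2.0 days, 0.3 | 0.938 | 0.978 | 1.010 |
| 2.5 days, 0.3 | 0.924 | 0.976 | 1.017 |
| 2.5 days, 0.4 | 0.914 | 0.976 | 1.03 |

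In hours, the daily-change row is about 0.5–0.9. At 2.0 days (CV 0.3) the medians are 1.872 and 1.757 days: 0.115 × 24 = 2.8 hours. At 2.5 days (CV 0.3) they are 2.309 and 2.134 days: 0.175 × 24 = 4.2 hours. At 2.5 days with CV 0.4 the loss is close to 5 hours.

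**6. Sensitivity.** A fixed daily habit gives 0.973. A 22-day Period 1 gives 0.973 (1.0 day, CV 0.2) and 0.888 (2.5 days, CV 0.4). Very erratic wear (CV 0.8, mean 2 to 3 days) gives about 0.85. The Period 2 median was the lower one in every scenario.

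**The case against.** Much of the case on the other side stands.

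- **Redaction.** A reader might infer that the plan has no rule for visit changes. The documents do not support that. Every endpoint row of Table 2 (section 6.1.1) and parts of the exploratory analysis text in section 7.1 are redacted, and a rule could be there. What can be said is that the visible sentences, followed literally, count these wears.
- **Existing safeguards.** The reason for change is recorded, and section 7.1 lets invalid data points be omitted with documentation. This supplies the means but does not name the case. Omission alone also leaves some bias at longer wear, because visits tend to interrupt long wears.
- **The factor of two.** It is tempting to treat this as fixed. It holds only at nominal lengths. The Table 2 footnote also limits some Period 1 entries to the first 14 changes. If that covers wear time, a daily changer with a long Period 1 might contribute no visit-ended wear there at all.
- **Size.** Section 6.2 expects daily change, which points to the low end of the range. The 9% figure needs wear close to the three-day limit.
- **Consequence.** A reader might infer a high risk of a falsely significant wear-time result. No test of wear time is visible, so any such error rate would rest on an analysis that the plan does not state. Wear time is not the primary endpoint, section 7.5 sets no success criteria, and the sequential unblinded design already limits how far a small contrast can be read. The bias also cannot create a false advantage for the test product.

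The direction of the shift and its mechanism remain.

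**Conclusion.** The point holds as a minor one. Under the visible derivation, and at nominal period lengths, identical products would give a Period 2 median about 2–4% shorter at daily change, and up to about 9% shorter with mean wear of 2.5 days and CV 0.4. The shift is against the test product and is confined to wear time.

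The count of one against four visit-ended wears comes from the documents. The percentages and hours rest on assumed wear distributions and should be read as a range. The conclusion is conditional on the redacted text not already containing a handling rule.

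**What to change.** If the redacted text already handles visit changes, confirm this and stop there. Otherwise add the following to the wear-time definition:

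- Flag each wear that ended at a site visit, using the visit date and the recorded reason for change.
- Treat flagged wears as right-censored at the visit, in both periods.
- Report the per-subject Kaplan-Meier median for each period, and compare the periods on that.
- Report the median with flagged wears simply excluded as a sensitivity analysis. It is close to the censored result at daily change and falls somewhat short at longer wear.
- State whether the limit of 14 recorded changes in Period 1 applies to wear time.

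Censoring is not exact: it overcorrects slightly at long wear (1.03 at 2.5 days, CV 0.4), but stays nearer to 1 than counting all wears. The cost is a few lines of text, a little more programming and slightly fewer fully observed wear times. No new data are needed.

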#### 6.1.5. Discussion of clinical investigation design

The new test product is intended for people with an ileostomy and for colostomists with liquid output. The two groups experience the same issues regarding leakage and skin problems and could therefore benefit from the product.

SenSura® Mio and SenSura® users are chosen and will be considered as one group, since results from a previous investigation showed no difference between the two user groups regarding inner circle TEWL (primary endpoint).

The duration of Test Period 1 (14 (-2/+15) days) and two test visits in the period is found adequate to assess baseline data on the wear time, leakage pattern and skin condition of the subject. The test product is tested for 28 (-4/+12) days to ensure that the skin will have time to adjust to the new conditions, reach a steady state, and for the subjects to test an adequate number of products to give a thorough evaluation of the products.

To follow safety closely and ensure proper compliance and no unexpected events related to the test product, the first five subjects will be enrolled at the Coloplast Humlebæk Site DK001 (Sponsor). In addition, and due to Christmas holiday, follow-up logistics and planning purpose, the following subjects, at other sites than DK001, will be invited for the test visit 1 during week 49-51 (December 2018) and for their test visit 2 during week 1 and 2 (January 2019).

 CP275 – A clinical investigation evaluating three new 1-piece ostomy products

Danish Ethical Committee registration number H-17005054/Danish Competent Authorities registration number DMA-2017022387

In this investigation, a part of the information about the products is obtained via interviews (qualitative data). The interviews allow for detailed questions (in the form why, when, how) that can be adjusted individually per each subject's experience. This gives more details about the subject's experience with the test product. However, some drawbacks also occur with this method of obtaining information, as the interview data is subjective and cannot be quantified. The interviews may also cause a positive bias towards Coloplast. Thus, in this explorative investigation, the main endpoints are obtained by CRFs (from all subjects) and the interviews are used for supplementary information. The data collected by interviews will be handled confidentially, as all other data collected in this investigation.

The investigation is not blinded because the test product and SenSura® Mio are visibly different from each other. If the subjects have a preconceived attitude to the test products or SenSura® Mio bias could occur for all subjective parameters.

## 6.2. Investigational device and comparator(s)

Subjects using 1-piece open products are expected to change their products every day. Therefore, they are expected to use 14 (-2/+15) of the comparator products during Test Period 1 and 28 (-4/+12) of the test products during Test Period 2.

To take the variety of visit windows, change patterns and distribution logistics to sites in different countries into account, a safety margin of products has been added. Therefore, the total number of products for this investigation is 2000 1-piece products.

The test product is based on the SenSura® Mio 1-piece products already on the market. Therefore, the comparator in this investigation is:

- 1-piece
  - SenSura® Mio 1-piece open, flat, maxi, neutral grey, 10-55 mm and circle filter

## 6.3. Subjects

To be included in the investigation, the subjects must comply with the selection criteria described in section 6.3.1 and must not comply with the exclusion criteria described in section 6.3.2.

### 6.3.1. Inclusion criteria for subject selection

Subjects interested in participating the clinical investigation must comply with the following criteria:

Inclusion criteria To be included the subjects must:	Justification To ensure that:
Have given written informed consent	the subject participates voluntarily
Have an ileostomy or a colostomy with liquid* output (as their usual output) * Bristol Scale: 6-7	• only subjects which the product is aimed for will be included
Be at least 18 years of age and have full legal capacity	• the subject is competent and that data quality is high

Have had their stoma for at least three months	
 
the initial post-operative problems are overcome, and that the subject is used to having an ostomy as well as changing the product before entering the investigation
 

Be able to use products with max cut size 45 mm	
 
[REDACTED]
 

Have self-reported problems with leakage** (three times within 14 days) **Leakage: Leakage is defined as output from the stoma on the backside of the baseplate/underneath the baseplate	
 
a potential change in leakage performance and skin condition can be observed
 

Handle the Clinical App, test product and comparator product themselves	
 
the subject can take pictures and complete the CRF questions in the app, in addition to handle the products
 

Use a flat SenSura® Mio or a flat SenSura® with standard adhesive as their current product Standard adhesive: Not extended wear adhesive	
 
the subjects will use a product with the same wear time
 

Minimum change of baseplate at least once every 3 rd day	
 
To ensure that subjects change the products sufficient times during the investigation
 

Are willing and suitable (determined by investigator/study nurse) to use the test product and comparator without using a paste/mouldable ring during the investigation	
 
a potential effect of the new baseplate cannot be detected
 

Are willing and suitable (determined by investigator/study nurse) to use a 1-piece product during the investigation	
 
to ensure compliance to the protocol during the investigation
 

### 6.3.2. Exclusion criteria for subject selection

Subjects complying with the following criteria must be excluded from participation in the clinical investigation:

Exclusion criteria	Justification
The subjects are not allowed to participate in case they:	
Are currently receiving or have within the past two months received radio-and/or chemotherapy (low doses chemotherapy are allowed for other indications than cancer, e.g. below 15 mg methotrexate for rheumatoid arthritis)	The skin undergoes major changes because of radio-and/or chemotherapy, and as a consequence, the skin might be more fragile to product changes.
Are currently receiving or have within the past month received topical steroid treatment in the peristomal skin area (e.g. lotion or spray) or systemic treatment* (e.g. injection or tablets).	Steroid product on peristomal skin may interfere with the skin condition. Use of steroid product can make the skin more fragile to baseplate change.
*Investigator will decide on case basis whether the treatment is accepted under the protocol	
Get a positive result of a pregnancy test for women of childbearing age/fertile**	Even though the ingredients and the recipes have been approved for humans, their effect on embryos, foetuses, and infants are unknown.

Are breast feeding	Even though the ingredients and the recipes have been approved for humans, their effect on embryos, foetuses, and infants are unknown.
Are participating in other interventional clinical investigations or have previously participated in this investigation  Exception: Participation in other Coloplast in-house clinical investigations is accepted under the circumstances that the subject has paused the activities in the investigation and are otherwise complying with the inclusion and exclusion criteria of this (CP300) protocol.	Other interventional investigation guidelines/products may interfere with these investigational endpoints. Some of the Coloplast studies are taking place over a two-year period, where the subjects will be paused for longer periods between the visits - therefore they can participate in other Coloplast studies meanwhile.
Have known hypersensitivity towards any of the products used in the investigation	It is not ethical to include persons that know they are allergic to the products used in the investigation and it would also create bias, as these persons would give the product they are allergic to a more negative rating and most likely also create an AE.

\*\* Besides a negative pregnancy test the women must also sign a document claiming that they will use safe contraceptives during the study period (i.e. contraceptive coil, hormone base contraceptives or surgical sterilisation). However, in some cases when the women are older than 50 years, but are not yet post-menopausal, the investigator may evaluate that it is not reasonable to ask these women to start using safe contraceptives for the duration of the investigation (e.g. if the subject is abstinent, the partner is surgically sterilised, or either subject or partner is infertile). In these cases, the investigator can include the women, but has a responsibility of ensuring that he/she has done what he/she can to prevent these subjects from becoming pregnant. As a minimum investigator, must talk to the women about the risk of and how to avoid unwanted pregnancy at inclusion.

### 6.3.3. Recruitment and enrolment

The recruitment of potential subjects will commence only once authorisation has been received from the Regulatory Authorities and the EC.

**Table 3: Table showing an overview of the recruitment process**

Recruitment method	Coloplast Database	Advertisement	Patient records
Potential subjects	Recruitment will go through Coloplast own subject database (stoma care users) in Denmark and Sweden. Potential subjects are identified by the following searching criteria in the Coloplast database: 
 
• Has an ileostomy or colostomy
 
• 1-piece or unspecified
 
• Open or unspecified
 
	Advertisement i.e. in local shops, sports facilities, local newspapers, social media and ostomy associations. The advertisement will state the contact information of relevant investigator(s) to contact. A CRO may help by receiving reply letters-mails and/or answering the phone from interested subjects.	Recruitment from hospitals, home care nurses and outpatient ostomy clinics will be via patient visit or screening of subject records kept at the participating sites.

	
 
• Be at least 18 years of age
 
		
First contact	
The identified potential subjects will as first contact be sent an Invitation and Reply Letter by mail or email.
	
Interested subject contact the investigator.
	
The identified potential subjects will be contacted and informed about the investigation by the investigator (via telephone, letter or e-mail).

	
If a potential subject does not return the reply letter or answer the email, they may be contacted by phone, mail or email to make sure that they have received the approach.
		
Second contact	
If potential subjects return the Reply Letter/reply to the email, or have called the investigator as first contact and are interested, the Investigator or delegated site personnel will contact the subjects by phone and give a short introduction to the investigation and go over the inclusion and exclusion criteria.
 
If the subjects do not meet the inclusion criteria or meet the exclusion criteria, this will be registered at the Subject Screening Log.
		
Subject Information Form	
If subjects are eligible and interested in participating, then written information about the investigation (subject information) will be sent to the subjects to ensure that they are given the opportunity to read about the investigation before a possible informational visit, and so that they can prepare any possible questions they may have. The subject information provides information to subjects about how to contact the investigator or a representative thereof, or a representative of the sponsor (name, telephone number and e-mail address), if they wish to learn more about the study.
		
First visit Information visit	
If an eligible subject is interested in participating after the first contact, a visit will be arranged in a room reserved to ensure privacy and quiet surroundings at the investigators clinic/department. When arranging the visit, it will be ensured, that the subject has received the Information Form prior to the visit. The subjects will receive both written and verbal information about the possibility of bringing a companion to the informational visit and to any possible subsequent visits.
 
See section 13 for information to be given to the subjects, as well as the informed consent process.
		
Enrolment and inclusion visit (V0)	
The subjects have the right to wait 24h before deciding on participation. If/when the subject decides to participate he/she will be asked to sign the relevant forms (see section 13). If a subject so desires, and it is certain that it is understood what the investigation entails and the relevant forms have been signed the subjects are considered enrolled in the investigation.
		

The first ten subjects will be enrolled at the Coloplast Humlebæk Site DK001 (Sponsor). When these ten subjects have completed the first 7-1/+3 days with the test product and completed the safety visit (V3) in proper compliance and with no unexpected events related to the test product, all following subjects can hereafter continue with enrolment and Test Period 2 at all sites.

The subjects, at other sites than DK001, will be invited for the Test Visit 1 during week 49-51 (December 2018) and for their Test Visit 2 during week 1 and 2 (January 2019), due to Christmas holiday, follow-up logistics and planning purpose. Hereafter, subjects will have 7-1/+3 days between their following visits.

The coordinating clinical manager will have close contact to each site during the recruitment period. The investigator at each site will notify the clinical manager of all planned inclusion visits and whenever a subject is enrolled. This will be done by mail and be site registration in a sheet for this purpose. When the coordinating clinical manager is aware that 25 subjects have been included, the recruitment will stop. Subjects who have been informed of the investigation and are reflecting on their participation may be included within the first 24 hours hereafter.

Enrolment period will be between 12-39 days for Test Period 1 and 284/+12 days for Test Period 2. Site should however ensure that the visit windows are adjusted for the subjects to be terminated at last LSLV, at the latest.

